**Pre-Procedure Medications**

- **Anticoagulation Therapy**

If the subject has been on direct oral anticoagulation (DOAC) therapy, medication should be stopped at least 24 hours prior to the implant procedure (following manufacturer’s guidelines for use) in both arms.

- *WaveCrest arm:* Subjects currently taking warfarin should suspend its use 3 days prior to the implant procedure. It is recommended but not required that the subject’s INR be <2.0 prior to the implant procedure. Warfarin may be discontinued less than 3 days prior to the implant procedure when the Investigator deems discontinuation to pose a significant risk to the subject (e.g., select subjects with a history of prior stroke or LAA thrombus, or a high CHA2DS2-VASc score). Within 24 hours of the implant procedure, 75-325mg aspirin should be administered.
- *Watchman arm:* Warfarin and aspirin use should be managed according to the Watchman DFU.
- If randomization will take place <3 days prior to the implant procedure, subjects taking warfarin pre-procedure should stop its use 3 days prior to the implant procedure. Warfarin may be discontinued less than 3 days prior to the implant procedure when the Investigator deems discontinuation to pose a significant risk to the subject (e.g., select subjects with a history of prior stroke or LAA thrombus, or a high CHA2DS2-VASc score).

- **Antibiotic Therapy**

Immediately before the implant procedure, the subject should receive routine prophylactic antibiotics per the site’s standard of care

**6.3 Implant Procedure**

Follow the Coherex WaveCrest LAA Occlusion System or the Boston Scientific Watchman LAA Occlusion System IFU/DFU, as applicable, for the implant procedure.

[REDACTED]

[REDACTED]

	Title: The WAVECREST 2 Trial  Clinical Investigational Plan	Doc. #: CHX_IP014	Rev: H
---	--	-----------------------------	------------------

4. [REDACTED]

Record the following information:

- Date of procedure, catheterization laboratory entry/exit time, procedure duration (see **Appendix I: Acronyms and Definitions**), device duration (see **Appendix I: Acronyms and Definitions**), device model number and serial number, date of implant, number of devices used, fluoroscopy and contrast volume used
- Warfarin and aspirin should be administered to Watchman arm subjects according to the product DFU. Per site/geographic standard of care, alternative vitamin K antagonists (e.g., acenocoumarol or phenprocoumon) may be used.
- Administer clopidogrel 75 mg to WaveCrest arm subjects within 12-48 hours, then daily post-procedure (prasugrel or ticagrelor are allowable for clopidogrel intolerance, however, prasugrel is contraindicated in subjects with a history of prior stroke/TIA and both prasugrel and ticagrelor are contraindicated in subjects with a history of hemorrhagic stroke). Administer aspirin (75-100 mg) within 24 hours, then daily post-procedure.
- Collect TEE/ICE images and submit images to ECL
- [REDACTED]
- Record cardiac medications, including antiplatelet and anticoagulant medications
- Record adverse events, device malfunctions and protocol deviations.

#### 6.4 Discharge

Before the subject is discharged from the hospital:

- Record adverse events, device malfunctions, and protocol deviations as appropriate
- If there is any concern for stroke, a Neurologist, blinded to subject's randomization and implanted device to the extent possible, must evaluate the subject before discharge. (See **Section 6.12** for details of **Unscheduled Neurology Visit**)
- Record cardiac medications, including antiplatelet and anticoagulant medications
- Watchman subjects should be discharged on warfarin and aspirin per the Watchman DFU. For subjects on dual antiplatelet therapy, who will also require warfarin, it is recommended that INR be targeted to 2.0-2.5.
- Discharge WaveCrest subjects on 75-100 mg aspirin daily and clopidogrel (prasugrel or ticagrelor are allowable for clopidogrel intolerance, however, prasugrel is contraindicated in subjects with a history of prior stroke/TIA and both are contraindicated in subjects with a history of hemorrhagic stroke).
- Table 3 summarizes the post-procedure anticoagulation and antiplatelet regimen for the duration of the trial.
- A physical exam (vital signs at a minimum) must be done prior to discharge.

	Title: The WAVECREST 2 Trial  Clinical Investigational Plan	Doc. #: CHX_IP014	Rev: H
---	--	-----------------------------	------------------

- A transthoracic echocardiogram (TTE) must be performed on all subjects to rule out a pericardial effusion prior to discharge.

**Note:** Subjects who are not implanted with a device must NOT undergo any additional LAA closure procedure with any device within 45 days of the initial implant procedure, except as randomized. At the discretion of the investigator, a second attempt to implant a subject as randomized may be made if there is reasonable medical justification to make such an attempt that is approved in writing by the Sponsor. All subjects, including those who fail to receive a device according to their randomization but who subsequently receive an alternate commercially available device or procedure will be followed with their initial randomization cohort according to an intent-to-treat analysis. The WaveCrest device may not be used among US subjects randomized to Watchman.

### 6.5 Follow-up Post-Discharge

Follow-up visits will be timed from the Treatment Visit. Following discharge after Treatment Visit, subjects will have office visits at 45 days, 6 months, 1 year, 2 years, 3 years, 4 years, and 5 years. Phone follow-up will occur at 3 months, 1.5 years, 2.5 years, 3.5 years and 4.5 years. Table 4 summarizes the schedule of assessments at each protocol-required follow-up visit. All assessments required for each visit must be completed within the visit windows specified in Table 5.

If a subject has experienced stroke symptoms resulting in a QVSFS score > 0 since their most recent follow-up, a board-certified study Neurologist blinded to subject’s randomization and implanted device, to the extent possible, must evaluate the subject or otherwise provide rationale for why an in-person neurology visit and exam are unnecessary. An **Unscheduled Neurology Visit** must be completed within 14 days of QVSFS administration or site’s awareness of the onset of stroke symptoms (See **Section 6.12** for details of the Unscheduled Neurology Visit).

Subjects who undergo a procedure but are not implanted with an LAA occlusion device must have follow-up per this CIP, with the following exceptions: TEE is not required at follow-up, and antiplatelet and anticoagulant medications should be administered following pre-procedure regimen or administered per physician discretion.

**Note:** Subjects will be followed as Intent-to-Treat. Any subject who does not receive an implant may not be treated with any other LAA device for 45 days.

The following sections describe the requirements for each follow-up office visit and phone follow-up for subjects implanted with an LAA occlusion device.

### 6.6 Follow-up 45 Day Office Visit

- Perform physical exam
- Administer QoL questionnaire (see **Quality of Life Questionnaire - SF-36**)

	Title: The WAVECREST 2 Trial  Clinical Investigational Plan	Doc. #: CHX_IP014	Rev: H
---	--	-----------------------------	------------------

- Qualified trial personnel who are blinded to subject’s randomization and implanted device administer the QVSFS (see **Appendix III: Questionnaire for Verifying Stroke-Free Status**). If the subject has experienced symptoms resulting in a QVSFS score > 0 since their most recent follow-up, a board-certified study Neurologist blinded to subject’s randomization and implanted device, to the extent possible, must evaluate the subject or otherwise provide rationale for why an in-person neurology visit and exam are unnecessary. This **Unscheduled Neurology Visit must be completed** within 14 days of the QVSFS administration or site’s awareness of the onset of stroke symptoms. (See **Section 6.12** for details of Unscheduled Neurology Visit)
- Perform a TEE following the Echocardiography Protocol and submit images to ECL.
- Cessation of warfarin in the Watchman arm is at physician discretion and should be per the product DFU. If the subject stops warfarin, clopidogrel should be administered per the product DFU.
- Evidence of device thrombus is recommended to be treated with a 6-week course of warfarin (+/- aspirin) and repeat TEE.
- Watchman subjects who discontinue warfarin should be instructed to remain on aspirin daily per the Watchman DFU.
- WaveCrest subjects must remain on dual antiplatelet therapy (DAPT) through 3 months post-procedure.
- Table 3 summarizes the post-procedure anticoagulation and antiplatelet regimen for the duration of trial follow-up.

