Post-Procedure Care	
Immediately post-procedure for 45 days post-implant:
 
 
• All subjects must have a TTE to rule out pericardial effusion prior to discharge.
 
• Subjects receiving a Watchman device should begin/continue/resume warfarin therapy and aspirin per the product Directions for Use (DFU). [Note: Alternative vitamin K antagonists (e.g., acenocoumarol or phenprocoumon) may be used according to geographic standard of care.]
 
• Subjects receiving a WaveCrest device are required to start clopidogrel 75 mg daily and 75-100 mg aspirin daily starting 12-48 hours after the procedure (prasugrel or ticagrelor are allowable for clopidogrel intolerance, however, prasugrel is contraindicated in subjects with a history of prior stroke/TIA and both prasugrel and ticagrelor are contraindicated in subjects with a history of hemorrhagic stroke).
 
 
45 days post-implant
 
 
• At 45 days (+15/- 5 days) post-implant, a device assessment with TEE is to be performed.
 
• Warfarin cessation in the Watchman arm is per Watchman DFU but is recommended if peri-device flow by TEE is <math>\leq 5</math>mm. If an adequate seal is not demonstrated, Watchman DFU recommendation for anticoagulation should be followed until peri-device flow <math>\leq 5</math>mm is observed.
 
• When Watchman arm subjects stop warfarin, clopidogrel should be started per the product DFU.
 
• Evidence of device thrombus in either arm is recommended to be treated with a 6-week course of warfarin (+/- aspirin) and a repeat TEE. For subjects in the WaveCrest arm, clopidogrel should be stopped prior to initiating anticoagulation therapy.
 
• Subjects treated with the WaveCrest device with no evidence of device thrombus will continue dual antiplatelet therapy (DAPT) regardless of peri-device flow until 3 months post-implantation.
 
 
3 months post-implant

	Title: The WAVECREST 2 Trial  Clinical Investigational Plan	Doc. #: CHX_IP014	Rev: H
---	--	-----------------------------	------------------

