### **3.6 Possible interactions with concomitant medical treatments and/or concurrent medical interventions**

No interactions are expected between the WaveCrest device and concomitant medications.

Oral anticoagulation is the standard of care to reduce the risk of stroke in people with atrial fibrillation. Subjects randomized to the Watchman arm should take post-implant medications

	Title: The WAVECREST 2 Trial  Clinical Investigational Plan	Doc. #: CHX_IP014	Rev: H
---	--	-----------------------------	------------------

according to the product DFU. This includes warfarin for 45 days post-implant, DAPT through 6 months post-implant, and 300-325mg of aspirin indefinitely. Alternative vitamin K antagonists (e.g., acenocoumarol or phenprocoumon) may be used according to geographic standard of care. In the WaveCrest arm, subjects will receive clopidogrel (or ticagrelor or prasugrel) and aspirin for at least 3 months. The combination of these medications may be associated with an increased risk of bleeding as compared to the risk when only one medication is used. Additional risks include:

- Internal bleeding
- Nose bleeds
- Bruising
- Prolonged bleeding from a cut or scrape
- Headache
- Upset stomach
- Nausea or vomiting
- Diarrhea
- Fever
- Skin rash
- Tissue death (necrosis)
- Decrease in white or red blood cells
- Inability to tolerate warfarin or aspirin
- Interaction with other medications or foods

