**Adjunctive Pharmacology Differences and Rationale**

WaveCrest subjects will receive DAPT between the point of implantation and 3 months post-implant (when clopidogrel can be discontinued). This is based on prior experience with the WaveCrest device that suggests a low stroke rate with this regimen. Subjects implanted with the WaveCrest device will be instructed to continue taking 75–100 mg aspirin throughout the study.

Watchman subjects are directed to take warfarin, clopidogrel, and aspirin based on that device’s DFU

Aspirin pharmacology studies have demonstrated maximal platelet inhibition with 50 mg of daily aspirin. The risk of gastric erosion increases as aspirin dosage increases. Aspirin 75 -100 mg in the WaveCrest arm has been selected to provide maximal platelet inhibition while minimizing the risk of gastric erosion and aspirin induced gastrointestinal bleeding.

- Record cardiac medications, including antiplatelet and anticoagulant medications
- Record adverse events, device malfunctions and protocol deviations as appropriate

	Title: The WAVECREST 2 Trial  Clinical Investigational Plan	Doc. #: CHX_IP014	Rev: H
---	--	-----------------------------	------------------

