### 6.7 3 Months Phone Follow-Up

- For subjects in the WaveCrest arm, if the LAA was closed at 45 days, instruct subject to discontinue clopidogrel but to continue aspirin at the assigned dosage.
- If the LAA was not closed at 45 days, clopidogrel may be continued at Investigator discretion until flow  $\leq 5$ mm is noted in a subsequent TEE.
- Record cardiac medications, including antiplatelet and anticoagulant medications.
- Record adverse events, device malfunctions, and protocol deviations as appropriate.

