# All Watchman adjunctive medication should be administered per the product DFU

† For subjects not implanted with a LAA occlusion device, antiplatelet and anticoagulant medications will be per physician discretion.

\* Alternative vitamin K antagonists (e.g., acenocoumarol or phenprocoumon) may be used according to geographic standard of care.

a Prasugrel 5-10 mg QD or ticagrelor 60-90 mg BID may be used in place of clopidogrel in subjects unable to take clopidogrel but may not be used with warfarin. Also, prasugrel is contraindicated in subjects with a history of prior stroke/TIA and both are contraindicated in subjects with a history of hemorrhagic stroke.

b If subject has remained on warfarin for non-closure, cessation of warfarin remains per Watchman DFU

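### The 45-day visit section keeps every WaveCrest subject on DAPT to 3 months, even with device thrombus, whereas the synopsis stops clopidogrel before warfarin

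*Protocol*

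**What the plan says.** **Synopsis, Post-Procedure Care, 45 days.** Device thrombus in either arm is recommended to be treated with six weeks of warfarin, aspirin optional, and a repeat TEE. Two statements then apply to the WaveCrest arm. The first is "For subjects in the WaveCrest arm, clopidogrel should be stopped prior to initiating anticoagulation therapy". The second, on who stays on DAPT, reads: "WaveCrest device with no evidence of device thrombus will continue dual antiplatelet therapy (DAPT) regardless of peri-device flow until 3 months post-implantation".

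**Section 6.6, 45-day office visit.** The same thrombus recommendation appears, without naming an arm: "Evidence of device thrombus is recommended to be treated with a 6-week course of warfarin (+/- aspirin) and repeat TEE". Two bullets later comes the DAPT rule: "WaveCrest subjects must remain on dual antiplatelet therapy (DAPT) through 3 months post-procedure". The section contains neither the instruction to stop clopidogrel nor the restriction to subjects without thrombus. The paragraph that follows, Adjunctive Pharmacology Differences and Rationale, repeats the 3-month DAPT course, also without condition.

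**Table 3.** WaveCrest warfarin is No at every visit, and clopidogrel is 75 mg daily at 45 days. No footnote deals with device thrombus. Footnote a says that prasugrel or ticagrelor "may be used in place of clopidogrel in subjects unable to take clopidogrel but may not be used with warfarin"; it is silent on clopidogrel with warfarin.

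**Section 6.7, 3-month call.** The only variation from stopping clopidogrel concerns non-closure: "If the LAA was not closed at 45 days, clopidogrel may be continued at Investigator discretion". Nothing covers a subject whose clopidogrel was already stopped for thrombus.

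**The concern.** The synopsis and the visit section give different antithrombotic regimens for the same patient at the same visit. The 45-day TEE is scheduled for all implanted subjects and is read for device thrombus, so this is a routine decision point.

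A site working from 6.6 has a recommendation to give warfarin and a mandatory statement to continue aspirin plus a P2Y12 inhibitor. Following both produces triple therapy, which the synopsis rules out. Section 3.6 cautions, about the post-implant drugs, that "The combination of these medications may be associated with an increased risk of bleeding". Major bleeding is a component of the primary safety endpoint, so any bleeds caused by the ambiguity would be counted there, in the WaveCrest arm.

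The conflict also leaves compliance undefined. A site that follows the synopsis departs from the *must* in 6.6, and a site that follows 6.6 departs from the synopsis.

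**Working it through.** The plan gives no figure to reproduce. The check is a comparison of the text, followed by two simple sizes.

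**1. Regimen for a WaveCrest subject with thrombus on the 45-day TEE**

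| Source | Warfarin | Aspirin | Clopidogrel |
|---|---|---|---|
| Synopsis | 6 weeks | optional | stopped before warfarin |
| 6.6 thrombus bullet alone | 6 weeks | optional | not mentioned |
| 6.6 DAPT bullet alone | not mentioned | continue to 3 months | continue to 3 months |
| Both 6.6 bullets | 6 weeks | continue to 3 months | continue to 3 months |
| Table 3, 45-day row | No | 75-100 mg | 75 mg daily |

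Only the synopsis states what happens to clopidogrel when warfarin starts. Triple therapy is not an explicit instruction anywhere. It results when both 6.6 bullets are applied as written.

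A subject taking prasugrel or ticagrelor meets a conflict within the body text itself: 6.6 requires DAPT to continue, while Table 3 footnote a forbids these drugs with warfarin. The synopsis stop instruction names only clopidogrel.

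**2. Length of the overlap under the literal reading**

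Inputs: 45-day window, days 40 to 60, and 3-month target day 91 with window days 76 to 121 (Table 5); six weeks = 42 days. Assumption: warfarin starts on the day of the TEE.

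Overlap = min(start + 42, end of DAPT) − start.

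- Start day 40: course ends day 82, before day 91, so 42 days.
- Start day 45: course ends day 87, so 42 days.
- Start day 60: course would end day 102, DAPT ends day 91, so 91 − 60 = 31 days.

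With DAPT to day 91 the overlap is 31 to 42 days. If DAPT instead ends at the 3-month call, the shortest case is 76 − 60 = 16 days, and the range is 16 to 42 days. Under the synopsis it is 0 days.

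**3. Number of subjects**

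Inputs: device thrombus in 2 of 92 during limited market release (section 2.7); 1,250 to 1,550 randomized 1:1 (SAP 8.5), so 625 to 775 WaveCrest subjects.

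- Rate: 2/92 = 2.17%, exact (Clopper-Pearson) 95% interval 0.26% to 7.63%.
- 625 × 2.17% = 13.6 (1.7 to 47.7).
- 775 × 2.17% = 16.8 (2.0 to 59.2).

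Section 2.7 does not say when the thrombi were found. Only those found before 3 months meet the DAPT conflict, so at that rate these counts are upper figures. Up to 500 roll-in subjects, all WaveCrest, are not included; at the same rate they would add 500 × 2.17% = about 11.

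**4. Later visits**

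Sections 6.8 to 6.10 repeat the thrombus recommendation without a stop instruction. By then a P2Y12 inhibitor is continued only for non-closure and at the investigator's discretion, so there is no opposing *must* and no contradiction.

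**The case against.** The strongest reply is that the protocol already contains the right rule. The synopsis addresses this exact case, and nothing in the body contradicts it about thrombus; 6.6 merely states the general rule and omits the exception. Moreover, the thrombus bullet in 6.6 makes aspirin optional. If mandatory DAPT also governed these subjects, that option would mean nothing in the WaveCrest arm before 3 months. On this view the coherent reading is that the thrombus regimen replaces DAPT.

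That reading is plausible, and it is probably what the sponsor intends. It does not remove the problem. Warfarin with continued DAPT also satisfies both bullets, one bullet is a recommendation while the other is mandatory, and the synopsis needed an express stop sentence to accompany the same recommendation. Section 6.4 gives an INR target for subjects on DAPT who also need warfarin. It sits among the Watchman discharge instructions, but it shows that the combination is not foreign to this protocol. Section 7.2 lets an investigator deviate to protect a subject, but it does not identify the intended regimen.

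Three other points have force. The 2/92 figure is a weak basis: the 92 include four unsuccessful implants, the number who had a follow-up TEE is not given, and scheduled TEEs could find more. Table 3 is a summary of default regimens, so its silence is an omission, not a conflicting instruction. And because the later visit sections contain no contradiction, a change there is optional.

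**Conclusion.** The concern holds. Section 6.6 and the rationale paragraph state an unconditional DAPT rule that is wrong, by the synopsis's own terms, for WaveCrest subjects with device thrombus at 45 days, and nothing else in the body corrects it. It should be fixed.

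The possible consequence is 31 to 42 days of warfarin plus DAPT per affected subject (16 to 42 if DAPT ends at the 3-month call), against none under the synopsis. This assumes that a site reads 6.6 literally and starts warfarin on the day of the TEE. The number affected is small and poorly known: about 14 to 17 randomized WaveCrest subjects if 2/92 applies, with exact limits from 2 to 59, before discounting thrombi found after 3 months and before counting roll-ins. The case rests on patient safety and clear instructions to sites; no effect on the 1.75 ratio test is claimed.

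**What to change.** 1. Restrict the 6.6 DAPT bullet, and the matching sentence in the rationale paragraph, to WaveCrest subjects with no device thrombus, as the synopsis does.
2. Add the synopsis stop instruction to the 6.6 thrombus bullet, worded for any P2Y12 inhibitor so that prasugrel and ticagrelor are covered. Align the synopsis sentence to match.
3. Add a Table 3 footnote in the WaveCrest columns: when warfarin is given for device thrombus, the P2Y12 inhibitor is stopped and aspirin is optional during the course.
4. Optionally, repeat the stop instruction in 6.8 to 6.10 for subjects still taking a P2Y12 inhibitor because of non-closure.

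The cost is a few sentences and one footnote in a protocol amendment. No visits, subjects or tests are added.

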**Adjunctive Pharmacology Differences and Rationale**

WaveCrest subjects will receive DAPT between the point of implantation and 3 months post-implant (when clopidogrel can be discontinued). This is based on prior experience with the WaveCrest device that suggests a low stroke rate with this regimen. Subjects implanted with the WaveCrest device will be instructed to continue taking 75–100 mg aspirin throughout the study.

Watchman subjects are directed to take warfarin, clopidogrel, and aspirin based on that device’s DFU

Aspirin pharmacology studies have demonstrated maximal platelet inhibition with 50 mg of daily aspirin. The risk of gastric erosion increases as aspirin dosage increases. Aspirin 75 -100 mg in the WaveCrest arm has been selected to provide maximal platelet inhibition while minimizing the risk of gastric erosion and aspirin induced gastrointestinal bleeding.

- Record cardiac medications, including antiplatelet and anticoagulant medications
- Record adverse events, device malfunctions and protocol deviations as appropriate

	Title: The WAVECREST 2 Trial  Clinical Investigational Plan	Doc. #: CHX_IP014	Rev: H
---	--	-----------------------------	------------------

